6.4.3 Sub-Group Analyses

As described in section [2.5.3](#), randomization will be stratified by child age for youth ages 5-12, 13-17, and 18-24 years old. Caregivers will be directly assigned to the child's randomization group (i.e., EMI or psychoeducation control). From a feasibility perspective, stratification will allow us to evaluate enrollment/retention data per age group across conditions (reducing the bias associated with enrollment/retention in a single arm treatment study), which will be useful to inform larger RCTs in the future. Stratification across ages will also better allow us to assess exploratory efficacy aims (see [6.4.5](#)) among developmental cohorts.

Further, as described in [6.4.2](#), we will evaluate demographic and medical/disease-related factors that are associated with components of feasibility.

6.4.4 Tabulation of individual Participant Data

Individual participant data will be listed by measure and time point.

6.4.5 Exploratory Analyses

Given the small sample, there may be limited power to detect changes on all exploratory outcome measures. Descriptive and summary statistics will be used to summarize secondary outcome measures between the EMI and control groups. Bivariate analyses (i.e., correlations, chi-square analysis as appropriate) will then be conducted to identify potential covariates for subsequent analyses. Dependent samples t-tests will assess changes pre- to post-intervention in child anxiety, depression, pain behavior, fatigue, mindfulness, and health-related quality of life among youth in the EMI group and also youth in the psychoeducational control group.

In addition, using dependent samples t-tests, we will explore changes pre- to post-intervention in caregiver anxiety, depression, stress, fatigue, sleep disturbance, psychological flexibility, mindfulness, and self-compassion among the intervention group and also parents in the psychoeducational control group. Given the small sample, these analyses will be considered hypothesis generating.

Linear regression models using the 8-week or 16-week assessment as the outcome will be considered in an effort to preliminarily estimate the effect size of the intervention, with

adjustment for potential confounders including scores at baseline. We will assess which demographic (e.g., age), medical, psychological, and environmental factors are related to preliminary efficacy of the intervention.

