2.6 BASELINE EVALUATION

Following parental consent and child assent, the parent/caregiver (see **Table 1**) and the participant (see **Table 2**) will complete a baseline assessment (Time 1) including questionnaires that assess their stress, emotional (e.g., depression, anxiety) and physical (e.g., pain, fatigue) wellbeing, in addition to baseline mindfulness/self-compassion. Disease parameters (e.g., cancer type and location, treatment history and radiation/chemotherapy doses, steroid use) will be abstracted from medical records. Participants will then be randomized to the enhanced mindfulness intervention (n=10 dyads) or a psychoeducation control group (n=10 dyads). The experimental design is depicted in **Figure 1**.

[figure not shown]

Figure 1 (See the Study Instrument 1 for descriptions of the measures).

2.6.1 Measures assessing caregiver (parent) functioning:

1. Demographic Questionnaire (5 minutes)

(see Study Instrument 1 for additional information regarding measures)

Table 1: Measures assessing parent functioning

Study Variable	Measure	Time Point	Time to Complete (approximate)
Self-compassion	The Self-Compassion Scale	All	10 minutes
Acceptance	Illness Cognition Questionnaire	All	< 5 minutes

Study Variable	Measure	Time Point	Time to Complete (approximate)
Mindfulness skills	Mindful Attention and Awareness Scale (MAAS)	All	5 minutes
Emotional well-being	PROMIS Emotional Distress: Anxiety and Depression, Short Forms 8a	All	5 minutes
Physical well-being	PROMIS Fatigue and Sleep Disturbance, Short Forms 6a	All	< 5 minutes each
Affect	Positive and Negative Affect Scale	All	5 minutes
Coping	Coping Inventory	All	<5 minutes
Feasibility	Feasibility Survey	Post-EMI	5 minutes
Total amount of time at each assessment			~ 35 minutes

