6.1.1 Primary Objective

The primary objective of this study is to assess the feasibility and acceptability of an enhanced mindfulness intervention in children and young adults (ages 5-24) with a high-grade or high-risk cancer and one of their primary caregivers. Feasibility and acceptability will be evaluated based on the following:

1. Proportion of eligible dyads who enroll during a two-year period
2. Treatment specific retention among all randomized participants, with a target retention rate of 70% over the 8 week EMI/control period
3. Compliance with at-home practices, with a proposed target rate of 4 out of 7 days per week on average over the 8 week EMI period
4. Parent and child reports of satisfaction on the feasibility questionnaire; for youth ages 8+ and caregivers, average item scores >3.0 will be deemed to reflect adequate feasibility

Of note, because the sample size of this study is very limited, even the results of the comparisons tested using statistical methods and identified within the primary objective will be considered descriptive and hypothesis generating.

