6.2 SAMPLE SIZE DETERMINATION

Sample size determination was not undertaken for this protocol because it is a small pilot intervention primarily aiming to test the feasibility of the proposed EMI. We specifically aimed to recruit 10 dyads per arm because this sample size would provide enough subjects to yield data appropriate for a pilot study. It is also anticipated that this sample can be recruited within a reasonable amount of time, over a 2 year period (1 to 2 dyads per month, on average). The proposed sample size will likely limit the ability to evaluate preliminary efficacy, which is an exploratory aim.

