6.3 POPULATIONS FOR ANALYSES

For the primary outcome of feasibility, all randomized participants will be included. In addition, as described below in section **6.4.2**, we will track total number of eligible individuals approached about the intervention (prior to randomization/enrollment), which will allow us to evaluate the proportion of eligible dyads who enroll. To evaluate exploratory aims, a modified intent-to-treat dataset will be used and will include all participants who, at a minimum, complete the initial in-person training (across EMI and psychoeducation conditions) and questionnaires at Time 1 (baseline) and Time 2 (8 weeks).

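### Section 6.4.5 lets an unspecified bivariate screen in 20 or fewer patients choose the covariates, beyond the baseline score, for the regression that estimates the EMI effect size

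*Combined protocol and SAP*

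**What the plan says.** Section 6.4.5 first summarizes the outcome measures by group and then says: "Bivariate analyses (i.e., correlations, chi-square analysis as appropriate) will then be conducted to identify potential covariates for subsequent analyses". The paired t-tests that follow take no covariates. The section then says: "Linear regression models using the 8-week or 16-week assessment as the outcome will be considered in an effort to preliminarily estimate the effect size", and specifies "adjustment for potential confounders including scores at baseline". The baseline score is therefore the only covariate fixed in advance.

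The pool to draw on is wide. Section 6.4.5 mentions demographic, medical, psychological and environmental factors, and section 2.6 adds: "Disease parameters (e.g., cancer type and location, treatment history and radiation/chemotherapy doses, steroid use) will be abstracted from medical records". Nothing limits candidates to variables measured before randomization.

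The data set is small. Section 6.2 says: "We specifically aimed to recruit 10 dyads per arm". Section 6.3 says: "To evaluate exploratory aims, a modified intent-to-treat dataset will be used", and requires the initial session plus questionnaires at Time 1 and Time 2. The retention objective in 6.1.1 is set "with a target retention rate of 70% over the 8 week EMI/control period".

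The plan is open about its limits. Section 6.2 expects the sample to restrict any look at efficacy, 6.4.1 treats testing as descriptive, and 6.4.5 regards its results as hypothesis generating.

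**The concern.** In a randomized comparison, covariates are not needed to remove confounding. They can improve precision, provided the choice does not depend on the data being analysed. Here the choice does depend on them, in a sample where one or two chance associations are expected from any list of reasonable length. The harm depends on what is screened:

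- **Against the pooled outcome.** If EMI works, arm is part of the outcome. A factor that differs between arms by chance then correlates with the outcome through arm, is selected, and takes over part of the EMI effect.
- **Against the outcome within arm.** Selected factors fit noise, so the residual variance and the standard error come out too small.
- **Against arm.** Selected factors are the ones most collinear with arm, so the variance of the arm coefficient rises.
- **Against the baseline score.** Little happens, because that score is already in the model.

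If the screen is run separately for each outcome, the adjustment sets can also differ between outcomes, and the effect sizes are then not on one footing. At stake is the estimate that 6.4.5 sets out to produce. Section 1.2.3 makes preliminary efficacy a step toward a larger, powered trial.

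**Working it through.** **Inputs from the plan.** 10 + 10 = 20 dyads (6.2). If retention only meets the target, 0.70 × 10 = 7 per arm (6.1.1). Two-sided alpha is 0.05 (6.4.1). The plan gives no effect size, SD, power or interval width, so there is no figure to reproduce.

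**Assumptions.** Within-arm SD 1; baseline–outcome correlation 0.5; 5, 10 or 20 candidates independent of arm; entry at p<0.05 (the alpha of 6.4.1, borrowed as a threshold) or p<0.20; true effect 0, 0.2, 0.5 or 0.8 SD. The age strata were not simulated.

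**Chance entries.** With K irrelevant candidates and threshold α, K × α enter on average: 5 × 0.05 = 0.25, 10 × 0.05 = 0.5, 20 × 0.05 = 1, 20 × 0.20 = 4. With 20 candidates at p<0.05, at least one enters in 1 − 0.95^20 = 64% of trials.

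**Reference model (arm + baseline score), 10 per arm.** Residual SD = √(1 − 0.5²) = 0.866, so SE ≈ 0.866 × √(2/10) = 0.39. Simulation gives 0.40, a mean estimate of 0.80 for a true 0.8, coverage 0.95 and median interval width about 1.65 SD.

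**Screened models, no candidate prognostic, true effect 0.8, entry at p<0.05** (Monte Carlo, mostly 6,000 to 20,000 trials per setting):

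| Screen | Per arm | Candidates | Mean estimate | Coverage | Other |
|---|---|---|---|---|---|
| Pooled outcome | 10 | 5 | 0.77 (−4%) | 0.95 | |
| Pooled outcome | 10 | 10 | 0.74 (−8%) | 0.94 | |
| Pooled outcome | 10 | 20 | 0.69 (−14%) | 0.93 | mean SE 0.388, SD 0.403 |
| Pooled outcome | 7 | 20 | 0.64 (−20%) | 0.92 | |
| Within arm | 10 | 20 | unbiased | 0.91 | SE 0.37, SD 0.44 |
| Arm | 10 | 20 | unbiased | about 0.95 | width 1.65 → 1.90 (+15%) |
| Baseline score | 10 | 10 | 0.80 | 0.95 | width 1.65 → 1.68 (+2%) |

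Percentages are relative to the true 0.80; for example, 1 − 0.691/0.80 = 14%.

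**Sensitivity of the pooled-outcome screen, 10 per arm.** At zero effect there is no bias and coverage is 0.95. A true 0.5 is estimated at 0.46 with 10 candidates and 0.42 with 20. A looser p<0.20 with 20 candidates gives 0.61 for a true 0.8 and 0.37 for a true 0.5, so over these 10-per-arm settings the shrinkage runs from about 4% to 27%. The mean SE stays within about 4% of the true SD, so the lost coverage is mostly bias.

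**When two candidates are prognostic (pooled-outcome screen, 10 per arm).** With 20 candidates the SD of the estimate falls from 0.400 to 0.378 and RMSE is 0.397 against 0.400. With 10 candidates, the two correlating 0.4 with the outcome, a true 0.8 is estimated at 0.705 with SD 0.355. RMSE is then √(0.095² + 0.355²) = 0.37, against 0.40 without screening. Variance falls, but the shrinkage remains.

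**The case against.** The strongest objection is textual. A reader might infer that the plan screens covariates against the outcomes, so that the EMI effect is biased toward zero and its interval is too narrow as well. The documents do not support that. Section 6.4.5 names correlations and chi-square tests but not the variable they are run against. Correlations suit the questionnaire scores. Chi-square needs categories on both sides, and arm is an obvious one; the word confounders also fits a check for imbalance between arms. The two harms also arise mainly from different screens: the pooled-outcome screen shrinks the estimate with a nearly correct SE, while the within-arm screen understates the SE without bias. A screen against arm widens the interval. This objection stands, and the point is conditional for that reason.

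Second, the sizes rest on chosen inputs. The plan says only that regression will be considered and that covariates are potential, so automatic entry of every factor below p<0.05 is an assumption. The largest bias at 10 per arm and that threshold, 0.80 − 0.69 = 0.11 SD, sits inside an interval about 1.65 SD wide. This also stands.

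Third, it would be wrong to say the screen can bring no precision gain. With prognostic candidates it lowers variance. Even with irrelevant ones (20 candidates, pooled-outcome screen, p<0.05), RMSE is √(0.109² + 0.403²) = 0.42 against 0.40 at a true 0.8, level at about 0.40 for a true 0.5, and √(0.030² + 0.381²) = 0.38 against 0.40 at a true 0.2, because shrinking toward zero helps when the truth is near zero. The case against that screen is avoidable bias and some lost coverage, not a large RMSE penalty.

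Fourth, the baseline score is already in the model, randomization is stratified by age, and the results are labelled hypothesis generating. These limit the consequence. The label warns about weak evidence, but it does not make a data-chosen adjustment preferable to a fixed one.

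**Conclusion.** The point holds in conditional form. Section 6.4.5 hands covariate choice, beyond the baseline score, to a screen whose target, candidate list and threshold are unstated, in at most 20 patients at planned size. With non-prognostic candidates, a pooled-outcome screen shrinks a true 0.8 SD effect by about 4% to 14% at 10 per arm (5 to 20 candidates, p<0.05) and by about 20% at 7 per arm with 20 candidates. With 20 candidates at 10 per arm, a within-arm screen gives coverage near 0.91 and an arm screen adds about 15% to interval width. A baseline-score screen costs about 2% in width with 10 candidates. If some candidates are prognostic, a pooled-outcome screen lowers variance and leaves RMSE about equal or somewhat lower, but the bias remains. No bias arises at zero effect.

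These figures depend on assumed candidate numbers, thresholds, correlations and effect sizes, and on leaving out the age strata. They do not show that this trial's estimate will be biased, only that the plan permits rules that would distort it and excludes none. Importance is modest, since the analysis is exploratory, but the effect size may be carried into planning the larger trial.

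**What to change.** In 6.4.5, stop using the bivariate analyses to select covariates for the arm comparison. Possible wording:

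> For every exploratory outcome, the EMI–control difference will be estimated by linear regression on arm and the baseline score of the same measure. The covariate set is fixed before outcome data are examined and is identical for all outcomes. Bivariate associations will be reported descriptively and will not determine the adjustment set.

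If wanted, the same sentence can name the randomization age stratum (5–12, 13–17, 18–24, per 6.4.3) or another variable measured before randomization. The age stratum takes two further degrees of freedom: residual 20 − 3 = 17 becomes 15 at full size, and 14 − 3 = 11 becomes 9 at 7 per arm. Any data-selected adjustment can be shown as a labelled sensitivity analysis.

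The cost is a few lines of text and no extra data. The downside is that a strong predictor found only in the data cannot enter the main estimate.

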1.1.2 Exploratory Objectives

- 1.1.2.1 To assess changes pre- to post-intervention in child anxiety, depression, positive and negative affect, stress, pain behavior, fatigue, mindfulness, and health-related quality of life compared to children in the psychoeducational control group.
- 1.1.2.2 To assess changes pre- to post-intervention in caregiver anxiety, depression, stress, fatigue, sleep disturbance, psychological flexibility, mindfulness, and self-compassion compared to parents in the psychoeducational control group.

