6.4 STATISTICAL ANALYSES

6.4.1 General Approach

For descriptive statistics, categorical data will be presented as percentages. Continuous data will be presented as means with standard deviations and ranges. For inferential statistics, statistical significance will be declared if $\alpha=0.05$ and tests will be two-tailed; results will be interpreted in the context of a pilot study in which statistical testing is for descriptive purposes. For exploratory analyses, checks of assumptions will be conducted and corrective procedures will be applied accordingly (e.g., transformation of non-normal data or nonparametric tests will be substituted).

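### The exploratory objectives ask for change relative to control, but the only tests of change committed to are paired t-tests within each arm; the between-arm model is optional

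*Combined protocol and SAP*

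**What the plan says.** Section 1.1.2 sets two exploratory objectives, both about change relative to control. The child outcomes are to be assessed "compared to children in the psychoeducational control group" and the caregiver outcomes "compared to parents in the psychoeducational control group".

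Section 6.4.5 then lists the analyses:

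- Between the arms, a description: "Descriptive and summary statistics will be used to summarize secondary outcome measures between the EMI and control groups".
- Covariate screening: "Bivariate analyses (i.e., correlations, chi-square analysis as appropriate) will then be conducted to identify potential covariates for subsequent analyses".
- Tests of change: "Dependent samples t-tests will assess changes pre- to post-intervention in child anxiety, depression" and the remaining child outcomes, in the EMI group and also in the control group. Caregiver outcomes get the same paired tests in each arm.
- A model that would estimate the intervention effect, adjusted for confounders including the baseline score: "Linear regression models using the 8-week or 16-week assessment as the outcome will be considered".

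The plan qualifies these analyses. Section 6.4.5 states "Given the small sample, these analyses will be considered hypothesis generating", and section 6.4.1 states that "results will be interpreted in the context of a pilot study in which statistical testing is for descriptive purposes". Section 6.2 accepts that the sample will probably restrict what can be learned about efficacy.

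**The concern.** The objectives pose a between-arm question, and the tests the plan commits to answer a within-arm one. A paired test asks whether one arm's mean change differs from zero. In this population it could do so through the course of disease, cancer treatment, regression to the mean or contact with the study team. Significance in one arm and not in the other is not evidence that the arms differ.

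The only analysis that addresses the objective is left open in three ways: whether it is done, at which time point, and with which covariates beyond baseline. No between-arm estimate with an interval is promised.

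Two features of the schedule make the open time point matter. Section 3.1 offers controls the EMI after Time 2 and expects the 16-week data to include some who took it, so a 16-week comparison may contain treated controls. Time 2 itself is stated inconsistently: sections 3.1 and 6.3 put it at 8 weeks, while section 3.2.2 lets the control group's Time 2 fall anywhere up to a year after baseline. If the arms were measured at different follow-up times, arm and elapsed time would be confounded.

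Section 3.1 gives preliminary efficacy data as one reason for a randomized pilot, and section 1.2.3 places a larger randomized trial after feasibility and preliminary efficacy have been established. The between-arm estimate is what the control arm adds on efficacy.

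**Working it through.** The documents contain no power or precision figure to reproduce; section 6.2 says no sample size determination was undertaken. The mismatch rests on the text alone. The calculations below only show its size.

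**Inputs from the documents:** 10 dyads per arm (6.2); two-tailed testing at 0.05 (6.4.1); 70% retention target (6.1.1), giving 0.70 × 10 = 7 per arm.

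**Assumptions:** the same true standardised change d (in SD of change) in both arms, so no intervention effect; normal data; independent arms; baseline-to-follow-up correlation r of 0.3 to 0.7.

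**1. How often within-arm tests point to EMI when the arms do not differ.** For a paired t-test, T is non-central t with n − 1 df and non-centrality d√n. Let u = P(T > t₀.₉₇₅) be the chance of a significant improvement, and q the chance of significance in either direction. The chance that EMI improves significantly and control is not significant is u(1 − q).

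Example, n = 10, d = 0.5: critical value 2.262, non-centrality 0.5 × √10 = 1.581, u = 0.2928, q = 0.2932. So u(1 − q) = 0.2928 × 0.7068 = 0.207.

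| d | n = 10 per arm | n = 7 per arm |
|---|---|---|
| 0 | 2.4% | 2.4% |
| 0.2 | 7.5% | 6.1% |
| 0.3 | 11.6% | 8.9% |
| 0.5 | 20.7% | 16.0% |
| 0.7 | 25.0% | 22.6% |
| 1.0 | 15.8% | 24.0% |
| 1.2 | 7.3% | 18.6% |

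The benchmark is a direct two-sided 0.05 test of the arm difference, which wrongly favours EMI 2.5% of the time at every d. There is no excess at d = 0. At 10 per arm the ratio is 0.0748/0.025 = 3.0 at d = 0.2, 0.2499/0.025 = 10.0 at d = 0.7 and 0.0733/0.025 = 2.9 at d = 1.2.

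Simulation (60,000 replicates per setting) agrees. Regression on arm, baseline and age wrongly favours EMI in 2.4% to 2.6% of trials for d from 0 to 0.7. With r = 0.5 and n = 10, the paired-test pattern occurs in 2.3%, 11.6%, 20.6% and 24.9% at d = 0, 0.3, 0.5 and 0.7.

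**2. What a committed between-arm estimate would deliver.** The 95% half-width, in SD of change:

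- Unadjusted: t(0.975, 2n − 2) × √(2/n). For n = 10: 2.101 × 0.447 = 0.94. For n = 7: 2.179 × 0.535 = 1.16.
- Adjusted for baseline and continuous age: t(0.975, 2n − 4) × √(2/n) × √((1 + r)/2). The last factor is residual SD over SD of change, √((1 − r²)/(2(1 − r))). It assumes equal variances, age unrelated to outcome and balanced covariates.

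| | r = 0.3 | r = 0.5 | r = 0.7 | Unadjusted |
|---|---|---|---|---|
| n = 10, formula | 0.76 | 0.82 | 0.87 | 0.94 |
| n = 10, simulated mean with chance imbalance | 0.80 | 0.86 | 0.91 | 0.93 |
| n = 7, formula | 0.96 | 1.03 | 1.10 | 1.16 |
| n = 7, simulated mean with chance imbalance | 1.03 | 1.11 | 1.18 | 1.14 |

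With two age-stratum terms instead of continuous age, the formula gives 0.77, 0.83 and 0.88 at n = 10, and 0.98, 1.05 and 1.12 at n = 7.

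An unadjusted t-test on change has 80% power only for differences of about 1.32 SD of change at 10 per arm and 1.63 at 7. An estimate with its interval is therefore more useful here than a test.

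**The case against.** The strongest reply is that the right model is already in section 6.4.5, with baseline adjustment and the stated purpose of estimating effect size. Nothing says that significance in EMI alone will be read as an intervention effect, so the percentages above describe a possible misreading and not the error rate of a planned decision. The plan repeatedly calls these analyses descriptive or hypothesis generating. It also commits to between-arm summaries with means and SDs and to individual data listings, so a between-arm estimate could still be recovered. Section 1.2.3 does not make the larger trial conditional on that estimate.

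Much of this stands, and it keeps the point modest. It does not remove it. The labels limit how strongly a result is claimed; they do not make a within-arm test answer a between-arm objective. An estimate recoverable afterwards is not prespecified, and the time point and covariates could be chosen with the data in view.

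Two further objections are partly right. The Time 2 conflict is a scheduling contradiction that would exist under any analysis; it matters here because it decides whether an 8-week comparison is valid, and it does not raise the importance of the point. Adjustment can also widen the interval if age enters as three strata that are unbalanced across arms: simulated means are about 0.95 against 0.93 at n = 10, r = 0.7, and about 1.2 against 1.14 at n = 7, r = 0.5. Randomization is stratified by age, however, and with balanced strata the corresponding figures are 0.89 and 1.08, both narrower than unadjusted.

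**Conclusion.** The point holds. The committed tests of change do not address objectives 1.1.2.1 and 1.1.2.2, and the analysis that would is optional in whether, when and with what adjustment it is done. If the true change is equal in both arms, the pattern most easily mistaken for an EMI effect occurs per outcome about 3 to 10 times as often as a direct test would err in EMI's favour, for d of 0.2 to 1.2 at 10 per arm. There is no excess when neither arm changes. These multiples depend on the assumed d; the textual mismatch does not. The primary feasibility result is unaffected. The correction should be made, because it is cheap and the efficacy comparison with control depends on it.

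**What to change.** In section 6.4.5:

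- For each exploratory outcome, commit to a linear regression of the 8-week (Time 2) score on arm and baseline score, with child age, the stratification factor, as a prespecified covariate in place of covariates found by bivariate screening.
- Report the adjusted EMI-minus-control difference with a 95% CI.
- Where Table 2 collects both self-report and caregiver report, name the reporter to be used.
- Keep within-arm changes as description.
- Treat any 16-week comparison between arms as descriptive, because controls may by then have received the EMI.
- Keep the hypothesis-generating label.

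Reconcile section 3.2.2 with sections 3.1 and 6.3 on the control group's Time 2, so that both arms are compared at the same follow-up time.

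The cost is wording, that reconciliation, and one degree of freedom for continuous age or two for three strata. No extra participants or data are needed. Intervals stay wide, roughly 0.8 to 0.9 SD of change either side at 10 per arm and 1.0 to 1.2 at 7. With continuous age or balanced strata, adjustment narrows them except at 7 per arm with correlation near 0.7. Self-report measures restricted to ages 8 and over will have fewer than 10 per arm if 5- to 7-year-olds enroll.

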2.5.4 Randomization and Arm Assignment

Patients, cohort 1, will be randomized between arms 1 and 2 stratifying for age. Once randomization of the patient has occurred their parent or primary caregiver, cohort 2, will be directly assigned to the arm in which their child was assigned.

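### The age strata used for randomisation are not prespecified in the exploratory between-arm regression, where covariates other than the baseline score are left to data-driven screening

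*Combined protocol and SAP*

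**What the plan says.** Section 2.5.4 says patients "will be randomized between arms 1 and 2 stratifying for age", and each caregiver takes the patient's arm. Section 6.4.3 gives the bands: "randomization will be stratified by child age for youth ages 5-12, 13-17, and 18-24 years old".

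Section 6.4.3 names two uses for the strata. The first is feasibility: "stratification will allow us to evaluate enrollment/retention data per age group across conditions". The second is efficacy by developmental cohort: "Stratification across ages will also better allow us to assess exploratory efficacy aims".

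The only model that compares the arms is in section 6.4.5. It is a linear regression of the 8-week or 16-week score that "will be considered in an effort to preliminarily estimate the effect size of the intervention", with "adjustment for potential confounders including scores at baseline". Before that, bivariate analyses are to pick out candidate covariates. Afterwards, age is mentioned as an example of a factor whose relation to preliminary efficacy will be examined. Nothing commits the plan to the age strata as model terms, and nothing excludes them. No confidence interval for the effect size is specified.

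Section 6.2 states "We specifically aimed to recruit 10 dyads per arm" and "Sample size determination was not undertaken for this protocol".

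**The concern.** A stratification factor is known before the first dyad is enrolled, so whether it belongs in the model should not depend on what the outcome data show. Stratifying removes age differences between the arms. If age is prognostic, the true variability of the arm estimate falls accordingly, but a model without the strata still counts the age variation as residual error. Its standard error is then too large and its interval too wide.

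At stake is the precision of the preliminary effect size. Section 1.2.3 plans a larger, adequately powered trial once feasibility and preliminary efficacy are established, so that estimate may well be carried forward. A second, smaller matter is that section 6.4.3 presents stratification as helping to assess efficacy within age cohorts, where the numbers are very small.

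**Working it through.** The plan gives no power, SD, effect size or interval width, so there is no figure to reproduce.

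**Inputs from the documents.** 10 dyads per arm, 20 in total (6.2); three age strata (6.4.3); two-tailed 0.05 (6.4.1); 70% retention target (6.1.1), giving 0.70 × 20 = 14; some child self-report scales limited to ages 8 and over (Table 2).

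**Assumptions.** Partial R² of age stratum given baseline: 0 to 0.30. Arms balanced within strata. Strata of equal size, since the documents give no quotas. n = 12 as an illustration of a scale restricted to ages 8 and over.

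**Interval width.** Arm + baseline leaves n − 3 degrees of freedom; adding two stratum indicators leaves n − 5. So

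width ratio (with strata ÷ without) = [t(0.975, n − 5) / t(0.975, n − 3)] × √(1 − partial R²)

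break-even partial R² = 1 − [t(0.975, n − 3) / t(0.975, n − 5)]²

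| n | t without strata | t with strata | Ratio at R² = 0 | 0.10 | 0.20 | 0.30 | Break-even R² |
|---|---|---|---|---|---|---|---|
| 20 | 2.110 (17 df) | 2.131 (15 df) | 1.010 | 0.958 | 0.904 | 0.845 | 0.020 |
| 14 | 2.201 (11 df) | 2.262 (9 df) | 1.028 | 0.975 | 0.919 | 0.860 | 0.053 |
| 12 | 2.262 (9 df) | 2.365 (7 df) | 1.045 | 0.992 | 0.935 | 0.875 | 0.085 |

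Example, n = 20 and R² = 0.20: (2.1314 / 2.1098) × √0.80 = 1.0103 × 0.8944 = 0.904.

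**Simulation check.** 6,000 trials per setting, assuming blocks of 2 within strata and a baseline correlation of 0.5. For R² of 0, 0.10, 0.20 and 0.30 the ratios were 1.017, 0.962, 0.903 and 0.844 at n = 20, and 1.043, 0.988, 0.926 and 0.863 at n = 14. These lie within about 0.02 of the formula. With the strata omitted and R² of 0.10-0.30, coverage of the nominal 95% interval rose to about 96-97.5%; with them included it stayed at about 95%.

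**Would the screen bring age in?** The plan gives no threshold. Assuming a correlation test at p < 0.05 with n = 20, the critical value is |r| = 2.101 / √(2.101² + 18) = 0.44, or about 20% of variance. If age explains 10% of variance, it passes about 28% of the time at n = 20 and about 20% at n = 14. The break-even for including the strata is far lower, at about 2% and 5%.

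**Within-stratum numbers.** 10 / 3 = 3.3 dyads per arm per stratum, or 7 / 3 = 2.3 at 70% retention. The 95% half-width of a between-arm difference with m per arm is t(0.975, 2m − 2) × √(2/m) SD:
- m = 3: 2.776 × √(2/3) = 2.27 SD
- m = 4: 2.447 × √(2/4) = 1.73 SD

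For retention, 2 of 3 has an exact 95% interval of 9% to 99%.

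**The case against.** A reader might infer that the arm model leaves age out, and that its interval is therefore wider than it needs to be. The documents support neither step. The covariate list is open, age is named as a factor to examine, and the screen could admit it. The loss depends on how well age predicts the outcome once the baseline score of the same measure is in the model, and no figure is given. The wide age range and age-tailored sessions make a link plausible but do not show one. The cost of two extra terms is also not always trivial: it reaches 3% to 4.5% at n = 14 to 12. And child age may say little about caregiver outcomes.

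A reader might also infer that section 6.4.3 plans efficacy tests within strata. It specifies no such test or contrast, so the 2.27 SD half-width describes an analysis that the plan does not commit to. Its first stated use of the strata, enrolment and retention by age group, is descriptive.

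Finally, the regression is only to be considered, the primary aim is feasibility without hypothesis testing, and the plan openly acknowledges limited power. Omitting the strata makes the test conservative, so it does not inflate false positives.

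All of this stands, and it limits the point to prespecification at low severity. It does not rescue the screen: a selection rule that would usually miss age at 10% of variance is a poor substitute for naming a factor already used to randomise.

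**Conclusion.** The point holds as a matter of prespecification. The strata are not named in the between-arm model, and their inclusion is left to the data.

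The effect on precision is conditional. At a partial R² of 10-20%, including the strata narrows the interval by about 4-10% at n = 20 and 2-8% at n = 14. If age is irrelevant, the interval widens by about 1% at n = 20, 3% at n = 14 and 4.5% at n = 12. Inclusion pays once age explains more than about 2%, 5% or 8.5% of residual variance respectively. These figures rest on the assumed range for age, balance within strata and, for n = 12, an illustrative count.

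Separately, about 3 dyads per arm per stratum, if strata are equal, cannot support an efficacy contrast within an age cohort. Severity is low, since the estimate is exploratory and any error from omission is in the conservative direction.

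**What to change.** **Section 6.4.5.** Fix the exploratory between-arm model in advance as: follow-up score = arm + baseline score of the same measure + randomisation age stratum (two indicators). State that covariates for this model are not chosen by bivariate screening. As a prespecified fallback where the analysed number is small, such as self-report scales limited to ages 8 and over, use a single linear age term, and list in advance the measures to which this applies. The fallback costs one degree of freedom: at n = 12, t(0.975, 8) / t(0.975, 9) = 2.306 / 2.262 = 1.019, about 2% wider if age is irrelevant, compared with 4.5% for two indicators.

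**Section 6.4.3.** State that results by age cohort are descriptive only and that no within-stratum efficacy contrast will be made, because of the numbers per cell.

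**Cost.** Wording only, with no change to recruitment, randomisation or data collection. The statistical price is one or two degrees of freedom. For caregiver outcomes the gain is less certain, but the same break-even values apply.
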